#### Inclusion Criteria:

- 1) Female
- 2) Ages 12-21
- 3) Sedentary- less than 2 hours of moderate (jogging, swimming etc) exercise a week.
- 4) BMI equal or greater than the 90th percentile for age and gender

5) PCOS per the most stringent NIH criteria adapted for adolescents (irregular menses >24 months post-menarche and clinical or biochemical hypertestosteronemia)

6) HS per FibroScan ultrasound, with CAP score of >225.

[figure not shown]
#### Exclusion Criteria:

1. Use of medications known to affect insulin sensitivity: metformin, oral glucocorticoids within 10 days, atypical antipsychotics, immunosuppressant agents, HIV medications, hormonal contraception. Dermal patch or vaginal ring contraception methods.
2. Currently pregnant or breastfeeding women. Development of pregnancy during the study period will necessitate withdrawal from the study.
3. Severe illness requiring hospitalization within 60 days
4. Diabetes, defined as Hemoglobin A1C > 6.4%
5. BMI percentile less than the 90th percentile for age and sex. Weight >325 lbs or <84 lbs.
6. Anemia, defined as Hemoglobin < 11 mg/dL
7. Diagnosed major psychiatric or developmental disorder limiting informed consent
8. Implanted metal devices that are not compatible with MRI
9. Use of blood pressure medications
10. Known liver disease other than NAFLD or AST or ALT >125 IU/L

[figure not shown]

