**Table 3: Composition of 15 g EAA nutritional therapy**

Histidine	6%
Isoleucine	11%
Leucine	23%
Lysine	16%
Methionine	5%
Phenylalanine	14%
Threonine	8%
Tryptophan	3%
Valine	14%

**Participants: Recruitment:** Girls will be recruited from several Children's Hospital Colorado clinics and from the community. Based on a 50% prevalence of HS in this patient population, up to 50 girls will be screened. Based on an approximately 5% drop out rate in my cross-sectional trials and my mentors clinical trials, we will aim to complete 20 girls with PCOS with HS. **Inclusion criteria:** PCOS per the most stringent NIH criteria adapted for adolescents (irregular menses >24 months post-menarche and clinical or biochemical hypertestosteronemia); age 12-21 years, sedentary status as exercise training affects IR (<2 hours of physical activity/week), BMI>90thile for age and sex, HS per FibroScan ultrasound, with CAP score of >225. **Exclusion criteria:** diabetes, liver disease other than NAFLD, liver transaminases >125 IU/L, medications affecting IR including metformin or hormonal contraception, hemoglobin <11 mg/dl, and MRI-incompatible metal.

**Aim 1: Hepatic steatosis and DNL:** IHTG percent will be assessed with MRI utilizing the Dixon method as in our previous studies. The Dixon method has excellent correlation with liver biopsy and is preferable to spectroscopy in obese participants, where spectroscopy coil depth of penetration is limiting. Visceral and subcutaneous fat will also be calculated from MRI as in our previous studies. Rates of hepatic DNL will be measured from the tracer incorporation of deuterated water into VLDL secreted palmitate with samples analyzed with GCMS by collaborator [name], as previously described in youth. We will utilize deuterated water rather than U-C13 acetate as in the APPLE study to reduce participant burden and blood volume draws. Further, both tracers have a carbon label and cannot be combined in a single protocol.

**Aim 2: Insulin resistance, hyperglycemia and hepatic glucose metabolism.** After 3 doses of overnight deuterated water (approximate times shown in **Figure 10**), participants will be given a U-C13 glycerol isotope drink per **Figure 10**. The glycerol drink is given in the morning while participant is fasting and

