### Overall enrollment procedure plan per group

#### VISIT 1 (SCREEN VISIT)

Pediatric CTRC Outpatient unit: Participants will begin with a medical screening and physical exam for inclusion/exclusion criteria evaluation. During this visit, patients will review and complete consent documents, have demographics and medical history confirmed, assess allergies and further evaluation of inclusion/exclusion criteria, have blood samples drawn, and have anthropometrics completed. HbA1c, ALT, AST, CBC panel and testosterone panel will be drawn at the beginning of the visit after consent in all participants. PCOS labs may be performed for confirmation of PCOS status, if not performed previously. Whole blood for DNA samples for future genetic analysis associated with hepatic steatosis will also be drawn and stored at this time. Participants will also have a Fibroscan (liver ultrasound) to check for HS (CAP score of >225).

After eligibility assessment, participants who qualify for the study will be randomized to placebo or EAA by the pharmacy. Both study staff and participant will be blinded. The participant will be scheduled for Visits 2 and 3 after being on placebo or EAA supplements for 4 weeks.

Screening lab test	Purpose for test
HbA1C	Rule out type 2 diabetes, if > 6.4% participant to be excluded
ALT, AST	Ensure no severe liver disease, if >125 IU/L participant to be excluded normal participant is excluded
Hemoglobin & Hematocrit (part of CBC)	If participant is Anemic, they will be excluded
Testosterone	Test for hyperandrogenism – required to meet NIH criteria for PCOS
Optional PCOS labs	
PCOS status must be confirmed prior to enrollment. Referring physicians often do not perform the entire recommend work-up for oligomenorrhea (per 2013 Endocrine Society Clinical Guidelines for PCOS). The values are typically expected in PCOS publications	
TSH, total T4	Ensure no hypo or hyperthyroidism causing amenorrhea
LH, FSH	Rule out primary ovarian failure
17-hydroxyprogesterone	Rule out late onset congenital adrenal hyperplasia
DHEAS	Rule out adrenal tumor
Prolactin	Rule out prolactin secreting brain tumor

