### **1. Blood Sampling**

**Description:** Blood will be drawn for Complete Blood Count (CBC), HbA1c, total and free testosterone, and sex hormone binding globulin. If participants have not had a full evaluation for oligomenorrhea, Prolactin, DHEAS, LH, FSH, TSH, total T4 or 17-OH progesterone may be drawn.

**Risk:** Minimal. Risk of pain, bruising at site of blood draw, excessive amount of blood.

**Minimizing Risk:** Certain studies at our institution draw over 7ml/kg in 6 weeks, or up to 7 ml/kg in a single draw, but include iron supplementation. Otherwise, the routine guidelines in our Pediatric CTRC are 2.5ml/kg for a single draw and no more than 5 ml/kg over a 4 week period. Our baseline visit will include 11.5 ml of blood (HbA1c, Hb, Cr, AST, ALT) and 25.5 ml of blood for PCOS patients (additional draw for T4, TSH, prolactin, LH, FSH, 17OH progesterone and DHEAS). The OSTT visit includes up to 300 ml of blood which will occur within 4 weeks of the initial visit. Thus, our OSTT visit is within the NIH Clinical Center guidelines of 9 ml/kg in 6-8 weeks and within Children's Hospital Colorado's institutional guidelines of 5 ml/kg. In addition, by study design, participants are screened by our baseline CBC and excluded if anemic, further increasing the safety of the study regarding blood draws. We will use a minimum weight cutoff of 38 kg to remain below the most conservative pediatric CTRC blood drawing guidelines. This screening also helps to increase the safety of the blood draw. In addition, the blood planned to be frozen and held could also be omitted if needed to reduce blood volume for a particular participant. Finally, our CTRC has a system to track other studies participants might enroll in, and we ask

during our consent process if the participant has been involved in any other studies in the past 6 weeks to avoid excessive blood drawing.

*Justification:* Screening laboratory measurements are necessary to assure that patients meet inclusion/exclusion criteria before any further study is completed. A CBC is necessary as a screening lab, to rule out anemia. A hemoglobin A1c can be used to rule out diabetes. Hormone levels of free and total testosterone, and sex hormone binding globulin are needed to categorize patients as having PCOS, and prolactin, DHEAS, LH, FSH, TSH, total T4 or 17-OH progesterone to rule out other causes of oligomenorrhea, if not done previously.

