### C. Participant Discontinuation Criteria

If a participant experiences any of the following, the participant will be withdrawn from the study.

1. Inability to complete study procedures
2. Abnormal screening labs (LFT's >125 IU, HbA1C>6.4%, Hg <11 mg/dL)
3. Participant becomes pregnant during study

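### The haemoglobin cut-off for anaemia is in mg/dL in all three places where it carries a number; 11 mg/dL is 0.011 g/dL, and 11 g/dL is almost certainly meant

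*Combined protocol and SAP*

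**What the plan says.** The combined protocol and SAP gives a numeric haemoglobin cut-off three times:

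- Section III.B, Exclusion Criteria, item 6: "Anemia, defined as Hemoglobin < 11 mg/dL".
- Section III.C, the Participants paragraph after the supplement composition table, which repeats the exclusions: "hemoglobin <11 mg/dl, and MRI-incompatible metal".
- Section VI.C, Participant Discontinuation Criteria, item 2, where haemoglobin is abbreviated to Hg: "Abnormal screening labs (LFT's >125 IU, HbA1C>6.4%, Hg <11 mg/dL".

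Two other places state the rule in words, without a number or unit. The haemoglobin row of the Visit 1 screening table says "If participant is Anemic, they will be excluded". Section III.D.1, Blood Sampling, says that "participants are screened by our baseline CBC and excluded if anemic, further increasing the safety of the study regarding blood draws", and its justification adds: "A CBC is necessary as a screening lab, to rule out anemia".

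**The concern.** Haemoglobin is ordinarily reported in g/dL, with values in the low to mid teens in this age group. A limit of 11 mg/dL lies far below anything compatible with life, so as printed it cannot separate anaemic from non-anaemic girls.

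Item 6 is the only definition of anaemia in the protocol. Anyone who wants a number for the worded rule in the screening table or in Blood Sampling has to take it from item 6 or from one of the two repeats, and all three have the same unit.

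What is at stake is participant safety and a clean audit trail. The screen covers girls as young as 12 who give up to 300 ml of blood at each of two overnight visits (Visits 3 and 5). A girl turned away at, say, 10 g/dL would not meet the criterion as written, so correct clinical practice would appear to depart from the protocol.

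**Working it through.** **Inputs.** The printed cut-off is 11 mg/dL (section III.B item 6, section III.C Participants, section VI.C item 2). Up to 50 participants may be enrolled for screening (section III.B). The conversion is 1 g = 1000 mg.

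**Step 1: the limit as written.** 11 mg/dL ÷ 1000 = 0.011 g/dL.

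**Step 2: the evident intended limit in the printed unit.** 11 g/dL × 1000 = 11,000 mg/dL.

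**Step 3: size of the discrepancy.** 11,000 ÷ 11 = 1000.

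**Step 4: is there a correct statement elsewhere?**

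| Place | Number and unit given |
|---|---|
| III.B Exclusion Criteria, item 6 | 11 mg/dL |
| III.C Participants, exclusion list | 11 mg/dl |
| VI.C Discontinuation, item 2 | 11 mg/dL |
| Visit 1 screening table, haemoglobin row | none |
| III.D.1 Blood Sampling | none |

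Three of three numeric statements use mg/dL and none uses g/dL, so no correct entry exists to override the wrong ones.

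**Step 5: consequence under each reading.** Under the literal reading, exclusion requires a haemoglobin below 0.011 g/dL, which excludes 0 of up to 50 girls. Under the reading 11 g/dL, the rule works as Blood Sampling describes.

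**Step 6: anything downstream?** The sample size statement in section VII rests on the change in liver fat and its standard deviation, and the analysis plan compares the two treatment periods within participants. Neither uses the haemoglobin threshold.

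**The case against.** The best case on the other side is that this is an editorial slip which nobody would follow. A limit of 0.011 g/dL is physiologically impossible, so it cannot be mistaken for a genuine alternative threshold. The screening table and Blood Sampling both say plainly that anaemic girls are excluded. That argument stands as far as expected practice goes: the zero-excluded figure describes the literal text and does not predict what would happen. It does not cure the error, because the worded rules supply no number.

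Two further points are fair and limit the weight of the finding. First, the anaemia screen is presented as an additional protection. The same section also sets volume limits per kg and a 38 kg minimum weight, allows stored samples to be omitted, and tracks participation in other studies. None of these depends on the haemoglobin unit. Second, the discontinuation rule refers to screening laboratory results, so it largely restates the Visit 1 check. The three occurrences are best seen as one slip repeated.

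A fault in reading the PDF is unlikely: the three statements sit in separate sections and differ in wording and capitalisation.

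**Conclusion.** The point holds, at minor severity. The cut-off is wrong by a factor of 1000 in every numeric statement. Read literally, neither the exclusion nor the discontinuation rule could ever apply. Read as 11 g/dL, both work as intended and nothing changes for participants.

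That the unit is wrong, and wrong in all three places, is certain. Two things are assumed. That 11 g/dL was meant rests on general clinical knowledge of how haemoglobin is reported, supported by the stated purpose of the screen; the documents do not say so. That staff would already apply 11 g/dL is probable but also not documented. The primary endpoint, power and analysis are unaffected.

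**What to change.** Change the unit from mg/dL to g/dL, so that the limit reads < 11 g/dL, in section III.B Exclusion Criteria item 6, the exclusion list under Participants in section III.C, and discontinuation criterion 2 in section VI.C. The investigator should confirm that 11 g/dL is the intended cut-off before the text is changed. Repeating the number and unit in the haemoglobin row of the Visit 1 screening table is optional, but it would let staff check eligibility from that table alone.

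The cost is a text correction in three places. Conduct does not change if 11 g/dL is already being applied.

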### **C. Study Design and Research Methods**

#### Overall Study Design:

Both aims will be accomplished from a cohort of 20 obese girls with PCOS and HS. Girls will complete a 12 week blinded placebo controlled cross-over study with 4 weeks each of EAA and placebo, with metabolic studies after each intervention and approximately 4 week wash out in-between (**Figure 9**). 4 weeks of EAA supplementation is adequate as it decreased IR and serum lipids in obese adults and IHTG can be changed within 3-9 days with more extreme dietary changes. Participants will have a total of 5 visits, a Screening visit (Visit 1) will ensure eligibility, Study 1 (Visits 2 and 3), and Study 2 (Visits 4 and 5) (see Study Calendar). The study days will include an abdominal MRI, OSTT with isotope tracers and assessment of other contributors to HS and IR. The study days (**Figure 10**) will start in the afternoon on day 1 with MRI measures, with at least a 4 hour fast prior, followed by admission to the hospital. Participants will receive deuterated water overnight, and in the morning, they will be given U-C glycerol drink while participants are fasting.

**Figure 10: Study day procedure timeline**

Blood will be drawn for DNL and gluconeogenesis. The oral sugar tolerance test (75g glucose +25g fructose) drink will be given a few hours later. A metabolic cart will be used to measure the rate of fat oxidation fasting, and throughout the OSTT. This is similar to our current PLUM study and it is well tolerated in youth.

**EAA Supplement:** The formulation of EAA (**Table 3**) is similar to our previous studies with an increased proportion of leucine, although we will give 10 grams of EAA twice a day, as this stimulates maximal protein synthesis. The increased leucine influences IR and also maximizes protein synthesis. Supplements will be given twice a day, once during the morning and the second in the evening, as balancing EAA intake across the day has a greater effect on protein synthesis and adolescents most frequently skip morning meals. The supplement is a powder that is mixed in 8 ounces of water. Placebo will be matched by the pharmacy to match the EAA supplement in flavor and appearance. Despite the dogma that excess protein challenges the kidney, long-term high protein diets do not affect kidney function in healthy individuals and we do not have safety concerns.

**Table 3: Composition of 15 g EAA nutritional therapy**

Histidine	6%
Isoleucine	11%
Leucine	23%
Lysine	16%
Methionine	5%
Phenylalanine	14%
Threonine	8%
Tryptophan	3%
Valine	14%

**Participants: Recruitment:** Girls will be recruited from several Children's Hospital Colorado clinics and from the community. Based on a 50% prevalence of HS in this patient population, up to 50 girls will be screened. Based on an approximately 5% drop out rate in my cross-sectional trials and my mentors clinical trials, we will aim to complete 20 girls with PCOS with HS. **Inclusion criteria:** PCOS per the most stringent NIH criteria adapted for adolescents (irregular menses >24 months post-menarche and clinical or biochemical hypertestosteronemia); age 12-21 years, sedentary status as exercise training affects IR (<2 hours of physical activity/week), BMI>90thile for age and sex, HS per FibroScan ultrasound, with CAP score of >225. **Exclusion criteria:** diabetes, liver disease other than NAFLD, liver transaminases >125 IU/L, medications affecting IR including metformin or hormonal contraception, hemoglobin <11 mg/dl, and MRI-incompatible metal.

**Aim 1: Hepatic steatosis and DNL:** IHTG percent will be assessed with MRI utilizing the Dixon method as in our previous studies. The Dixon method has excellent correlation with liver biopsy and is preferable to spectroscopy in obese participants, where spectroscopy coil depth of penetration is limiting. Visceral and subcutaneous fat will also be calculated from MRI as in our previous studies. Rates of hepatic DNL will be measured from the tracer incorporation of deuterated water into VLDL secreted palmitate with samples analyzed with GCMS by collaborator [name], as previously described in youth. We will utilize deuterated water rather than U-C13 acetate as in the APPLE study to reduce participant burden and blood volume draws. Further, both tracers have a carbon label and cannot be combined in a single protocol.

**Aim 2: Insulin resistance, hyperglycemia and hepatic glucose metabolism.** After 3 doses of overnight deuterated water (approximate times shown in **Figure 10**), participants will be given a U-C13 glycerol isotope drink per **Figure 10**. The glycerol drink is given in the morning while participant is fasting and

samples are collected at frequent intervals per **Figure 10** for positional NMR isotopomer analysis by collaborator [name] at UT Southwestern. Analyses will include modeling metabolic flux utilizing custom designed software and endpoints will include rates of excess TCA cycling contributing to triglyceride synthesis and gluconeogenesis as shown in **Figure 8**. This will be followed by a OSTT (75-gram glucose and 25-gram fructose) with frequent sampling of glucose, insulin, C-peptide. Fasting insulin sensitivity will be calculated with HOMA-IR (fasting glucose\* fasting insulin/22.4). The Matsuda index will be used to estimate whole body post-prandial insulin sensitivity and indices of hepatic [Glucose0–30(AUC)/insulin0–30(AUC)] and muscle insulin sensitivity [dGlucose/dtime ÷ insulin] with calculations starting at the downslope of glucose concentration. Blood glucose will be measured at the 2 hour time point and >140 mg/dL is defined as impaired glucose tolerance. Rates of fasting gluconeogenesis will be measured from the tracer incorporation of deuterated water into glucose, with samples analyzed with GCMS by collaborator [name], as previously described in youth. **Metabolomics:** Targeted amino acid and amino acid breakdown product metabolomics profiles will be measured by the University of Colorado metabolomics core on fasting and 120 minute post glucose drink samples (<https://www.dalessandrolab.com/home>).

Study Calendar	Screen	Phase I		Phase 2	
	Visit 1	Visit 2 –MRI	Visit 3 – Overnight	Visit 4 –MRI	Visit 5 – Overnight
Consenting and Eligibility Assessment	X				
History & Physical	X				
Intravenous Blood Draw	X		X		X
Fibroscan -Liver ultrasound	X		X		X
Randomization- Placebo vs EAA	X				
Crossover- Placebo vs EAA			X		
Accelerometer teaching	X				
Gut Bacteria Collection			X		X
Urine Pregnancy Test			X		X
Questionnaires- SEARCH Food frequency, Activity 3DPA, Strengths and Difficulties and Sleep assessments			X		X
DEXA Scan (located in Leprino building)			X		X
Oral Glycerol Tracer with D 2 O			X		X
Oral Sugar Tolerance Test (OSTT)			X		X
WatchPAT sleep study			X		X
Metabolic Cart			X		X
EndoPat and Dynapulse		X		X	
MRI of abdomen and liver		X		X	
P MRS of Liver		X		X	
Total Time of visit (approximately)	2 Hours	2 Hours	22 Hours	2 Hours	22 Hours
Location of Visit	CHCO CTRC Outpatient	UCD Outpatient, Brain Imaging Center	CHCO or University Hospital Inpatient	UCD Outpatient, Brain Imaging Center	CHCO or University Hospital Inpatient

**Timeline:** The time between the initial screening visit and completion of the study will be less than 6 months. After confirmation of eligibility and randomization, participants will be on 4 weeks of EAA or placebo and then Phase I study visits will be completed (Visits 2 and 3). There will be approximately 4-

week washout period and then participants will crossover treatment, and complete another 4 weeks of EAA or placebo. Phase II study visits (Visits 4 and 5) will be completed.

### Overall enrollment procedure plan per group

#### VISIT 1 (SCREEN VISIT)

Pediatric CTRC Outpatient unit: Participants will begin with a medical screening and physical exam for inclusion/exclusion criteria evaluation. During this visit, patients will review and complete consent documents, have demographics and medical history confirmed, assess allergies and further evaluation of inclusion/exclusion criteria, have blood samples drawn, and have anthropometrics completed. HbA1c, ALT, AST, CBC panel and testosterone panel will be drawn at the beginning of the visit after consent in all participants. PCOS labs may be performed for confirmation of PCOS status, if not performed previously. Whole blood for DNA samples for future genetic analysis associated with hepatic steatosis will also be drawn and stored at this time. Participants will also have a Fibroscan (liver ultrasound) to check for HS (CAP score of >225).

After eligibility assessment, participants who qualify for the study will be randomized to placebo or EAA by the pharmacy. Both study staff and participant will be blinded. The participant will be scheduled for Visits 2 and 3 after being on placebo or EAA supplements for 4 weeks.

Screening lab test	Purpose for test
HbA1C	Rule out type 2 diabetes, if > 6.4% participant to be excluded
ALT, AST	Ensure no severe liver disease, if >125 IU/L participant to be excluded normal participant is excluded
Hemoglobin & Hematocrit (part of CBC)	If participant is Anemic, they will be excluded
Testosterone	Test for hyperandrogenism – required to meet NIH criteria for PCOS
Optional PCOS labs	
PCOS status must be confirmed prior to enrollment. Referring physicians often do not perform the entire recommend work-up for oligomenorrhea (per 2013 Endocrine Society Clinical Guidelines for PCOS). The values are typically expected in PCOS publications	
TSH, total T4	Ensure no hypo or hyperthyroidism causing amenorrhea
LH, FSH	Rule out primary ovarian failure
17-hydroxyprogesterone	Rule out late onset congenital adrenal hyperplasia
DHEAS	Rule out adrenal tumor
Prolactin	Rule out prolactin secreting brain tumor

